#### **2.2.4. Clinical Studies with Bimatoprost SR**

Study 192024-041D was a Phase 1/2 paired-eye comparison study evaluating the safety and efficacy of 4 dose strengths of Bimatoprost SR (6, 10, 15, or 20 µg [2 x10 µg implants]), as single or repeat administrations in 1 eye (study eye), versus the use of topical LUMIGAN 0.03% once daily in the contralateral eye (nonstudy eye). The objective of the study was to evaluate the safety and IOP-lowering efficacy of Bimatoprost SR in participants with OAG.

A total of 109 participants received at least a single administration of Bimatoprost SR, and 24 participants received a repeat administration of their initial Bimatoprost SR dose strength. A trend in dose response was observed across the 4 dose strengths that were tested. Data collected in this study suggested that the implant would provide topical prostaglandin analog-like efficacy up to 3 to 4 months after implantation in the majority of participants. Data following the second administration in the retreated participants showed similar IOP-lowering efficacy to that observed following the first administration of Bimatoprost SR.

There have been 2 generations of the Bimatoprost SR implant: the original Generation 1 formulation, and Generation 2, which is the formulation currently used in the Phase 3 studies. Among all Generation 2 dose strengths, most participants (> 66%) were still maintained on monotherapy with the initial Bimatoprost SR implant by Month 6. Additionally, at least 33% of participants had not received rescue topical IOP-lowering medication or a second Bimatoprost SR administration by Month 12. At Month 24, at least 23% of participants had not received rescue IOP-lowering treatment or a second administration of Bimatoprost SR.

Bimatoprost SR showed an acceptable safety profile with single and repeat administrations in Study 192024-041D. Most AEs were ocular, mild or moderate in severity, occurred within the first 2 days after Bimatoprost SR administration, and were considered related to the study drug administration procedure. There were no reports of serious study drug-related AEs, and no new safety concerns were observed after the second treatment that were not already known from the initial administration of Bimatoprost SR. Please refer to the investigator's brochure for details on reported safety findings.

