### **7.3. Lost to Follow Up**

A participant will be considered lost to follow-up if he or she repeatedly fails to return for scheduled visits and is unable to be contacted by the study site.

The following actions must be taken if a participant fails to return to the clinic for a required study visit:

- The site must attempt to contact the participant and reschedule the missed visit as soon as possible and counsel the participant on the importance of maintaining the assigned visit schedule and ascertain whether the participant wishes to and/or should continue in the study.
- Before a participant is deemed lost to follow-up, the investigator or designee must make every effort to regain contact with the participant (where possible, 3 telephone calls, and if necessary, a certified letter to the participant's last known mailing address or local equivalent methods). These contact attempts will be documented in the participant's medical record.
- Should the participant continue to be unreachable, he/she will be considered to have withdrawn from the study.

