## 9.2. Sample Size Determination

The sample size is based on practical considerations. Approximately 35 participants will be enrolled: 25 to 30 in the Bimatoprost SR cohort and 5 in the LUMIGAN 0.01% cohort.

Twenty-five to 30 participants will be enrolled in the Bimatoprost SR cohort to achieve a minimum total of 20 evaluable participants, defined as participants with sufficient data at baseline and Week 8 to evaluate the 24-hour IOP-lowering effect of Bimatoprost SR. This assumes a premature discontinuation rate of up to 33%. Participants who prematurely discontinue from the study will not be replaced.

Participants will be assigned to the Bimatoprost SR or LUMIGAN 0.01% cohort by the investigator.

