1.2.4. End of Study Definition

The end of the study is defined as the date of the last visit of the last participant in the study or last scheduled procedure shown in the SoA for the last participant in the study.

A participant assigned and treated with Bimatoprost SR is considered to have completed the study if he/she has completed all visits of the study to Month 12. At the Month 12/Study Exit visit, if the investigator determines that any safety concerns warrant participant follow-up, the participant may be followed post exit until safety concerns are resolved based on the investigator's discretion. Participants assigned and treated with LUMIGAN 0.01% may early

exit the study after completion of the Week 8 Sleep Lab visit, if there are no safety concerns in the opinion of the investigator. For the LUMIGAN cohort, an exit visit will be performed after the Week 8 Sleep Lab visit where all assessments scheduled for the Month 12/Study Exit visit will be performed.

2. Statistical Hypotheses

There are no statistical hypotheses for this study.

3. Sample Size Determination

The sample size is based on practical considerations. Approximately 35 participants will be enrolled: 25 to 30 in the Bimatoprost SR cohort and 5 in the LUMIGAN 0.01% cohort.

Twenty-five to 30 participants will be enrolled in the Bimatoprost SR cohort to achieve a minimum total of 20 evaluable participants, defined as participants with sufficient data at baseline and Week 8 to evaluate the 24-hour IOP-lowering effect of Bimatoprost SR. This assumes a premature discontinuation rate of up to 33%. Participants who prematurely discontinue from the study will not be replaced. Participants will be assigned to the Bimatoprost SR or LUMIGAN 0.01% cohort [REDACTED].

4. Populations for Analysis

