5.3.4.2. Time-to-Event Analysis

Time to the event of the initial use of nonstudy rescue IOP lowering treatment (medication and/or procedure) in the study eye from the date of Bimatoprost SR treatment will be estimated using Kaplan-Meier (KM) method with graphical display.

Time to initial use of nonstudy rescue IOP lowering treatment = (Date of initial use of non-study IOP-lowering treatment – Date of the Bimatoprost treatment) + 1.

In the calculation of time to initial use of nonstudy rescue IOP lowering treatment, if a participant did not use any nonstudy rescue IOP lowering treatment in the study eye, then the event (initial use of nonstudy rescue IOP lowering treatment) time will be censored at the study exit date or the last visit date if the study exit date is not available.

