5.4.1. Study Duration

The study treatment duration will be calculated as the number of days between the study exit date and Day 1 treatment administration day, inclusively (date of study exit or last visit available – Day 1 + 1).

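### The Kaplan-Meier rule for time to rescue prefers an undefined study exit date to the last visit, so a participant lost to follow-up can be counted as rescue-free through time that nobody observed

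*SAP*

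**What the plan says.** SAP 5.3.4.2 defines time to initial nonstudy rescue treatment in the study eye, counted from the date of Bimatoprost SR treatment, and says it "will be estimated using Kaplan-Meier (KM) method with graphical display". A participant with no recorded rescue is "censored at the study exit date or the last visit date if the study exit date is not available". The exit date therefore comes first, and the last visit is only a fallback. SAP 5.4.1 uses the same order for study duration ("date of study exit or last visit available"), and SAP 6.3.7.2 uses it for stop dates of ongoing medications. No section of either document says how the exit date is determined.

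Two protocol sections bear on when the two dates differ:

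- **Protocol 7.2** asks sites to carry out the Month 12/Exit procedures at the last visit of anyone who leaves early.
- **Protocol 7.3** covers those who stop attending. The site reschedules, telephones up to three times where possible and, if necessary, sends a certified letter. Only then: "Should the participant continue to be unreachable, he/she will be considered to have withdrawn from the study". No time limit is set.

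Rescue use becomes known through concomitant medications and procedures. These are collected at the scheduled visits and the Day 8 call (Protocol 1.3, Tables 1-1 and 1-2; Protocol 10.8.5).

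**The concern.** A Kaplan-Meier risk set should contain only people whose event would be seen if it happened. Once a participant stops attending, a rescue treatment started elsewhere cannot reach the database. If that participant stays in the risk set until a later exit date, the denominator includes someone who cannot contribute an event. The estimated rescue hazard falls and the rescue-free curve rises. The error can go only in that direction, which favours the implant, and a larger sample would not remove it.

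The target days in SAP Table 6-1 show how long such a gap could be. From Week 8 on they are 56, 112, 180, 270 and 360, so successive visits are 56, 68, 90 and 90 days apart. As an illustration, take someone last seen on Day 180 who misses Day 270 and is declared lost on an assumed Day 300. If Day 300 is entered as the exit date, the rule credits 300 − 180 = 120 unobserved days as rescue-free.

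What is at stake is how far the later part of this curve can be trusted as a description of how long the effect lasts.

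**Working it through.** **The plan's own figure.** The documents state no number for this analysis. The nearest design figure is the cohort size in SAP Section 3: "Twenty-five to 30 participants will be enrolled in the Bimatoprost SR cohort to achieve a minimum total of 20 evaluable participants". Protocol 9.2 adds "This assumes a premature discontinuation rate of up to 33" percent. Check: 20 / (1 − 0.33) = 29.9, which rounds up to 30 and matches the upper end. The lower end, 25, gives 20 evaluable at 20% discontinuation (25 × 0.80 = 20). The 33% covers every reason for leaving and is not a loss-to-follow-up rate.

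**Inputs**

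- *Rescue-free levels (illustrative):* S(6) = 0.66 and S(12) = 0.33, from the Phase 1/2 results in Protocol 2.2.4. The source gives more than 66% at Month 6, and "at least 33% of participants had not received rescue topical IOP-lowering medication or a second Bimatoprost SR administration by Month 12". Both are lower bounds, and the second also counts retreatment as an event.
- *Share lost by Month 12 (d):* not in the documents. Assumed 5%, 10%, 20% and 33%; the last treats every discontinuation as a loss.
- *Gap from last observation to exit date (L):* not in the documents. Assumed 1 and 3 months, with 6 months as a stress case.
- *Loss is unrelated to rescue risk:* assumed.

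**Formulas**

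- Rescue hazard: λ₁ = −ln(0.66)/6 = 0.0693 per month to Month 6, then λ₂ = −ln(0.33/0.66)/6 = 0.1155 per month.
- Loss hazard: μ = −ln(1 − d)/12.
- Share still observed and event-free: R(t) = S(t)·exp(−μt).
- Share in the risk set but unobserved: G(t) = ∫ μR(u) du over the last L months.
- Large-sample Kaplan-Meier limit: S*(t) = exp(−∫ λ(u)·R(u)/[R(u) + G(u)] du).

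**One case by hand.** Take d = 0.10 and L = 3. Then μ = 0.00878. Late in follow-up, G/R = μ(e^{(λ₂+μ)L} − 1)/(λ₂ + μ) = 0.00878 × (e^{0.373} − 1)/0.1243 = 0.032. The late hazard is therefore understated by about 3%. Integrated over the year, S*(12) = 0.340 against a true 0.330.

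**Month 12 estimate under the exit-date rule (true value 0.330)**

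| Lost by Month 12 | Gap 1 month | Gap 3 months | Gap 6 months |
|---|---|---|---|
| 5% | 0.332 | 0.335 | 0.340 |
| 10% | 0.333 | 0.340 | 0.351 |
| 20% | 0.337 | 0.351 | 0.373 |
| 33% | 0.342 | 0.368 | 0.406 |

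With a gap of zero, which is censoring at the last observation, the method returns 0.660 at Month 6 and 0.330 at Month 12.

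**Two cross-checks**

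1. A simulation placed the last attended visit at Day 56, 112, 180 or 270 with equal probability and the exit date at the next target day. It gave 0.340, 0.351 and 0.368 at Month 12 for 10%, 20% and 33% lost, the same as the 3-month column. Adding 30 or 60 days of contact attempts raised these to about 0.344 or 0.347, 0.359 or 0.367, and 0.381 or 0.393.
2. With n = 30 and 4,000 replicates, the mean estimate moved from 0.331 to 0.341 (10% lost, 3 months) and from 0.332 to 0.370 (33% lost, 3 months). The SD of a single estimate was 0.088 to 0.099.

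**The case against.** The strongest reply is that the exit date may simply be the date of the exit visit. Elsewhere the documents use study exit as the name of a visit. Protocol 7.2 puts exit procedures at the last visit, and SAP 5.4.6.4, for endothelial cell density, equates a participant's last visit with the exit assessment. On that reading, someone who disappears has no exit date, the fallback applies, and the rule already does the right thing. This stands as a possible reading, and under it the bias is zero. It is not secured by the text. Protocol 7.2 cannot help when no last visit takes place under that label, the SAP 5.4.6.4 sentence concerns one safety variable, and Table 1-2 (footnote e) has the site register withdrawals in the IWRS, which could produce a later date. The documents do not say which date is entered.

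A reader might infer that the curve *is* too high, or that the exit date is an administrative one. Neither is stated, so the bias is conditional. A reader might also take 33% as the expected loss. It is an all-cause allowance made to keep 20 participants evaluable at Week 8, so it serves only as an extreme. Nor is this the only evidence on durability, since Hour 0 IOP is summarised by visit through Month 12 (SAP 5.3.4.3).

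It is also fair to say that little depends on it. The endpoint is listed among the other efficacy endpoints in SAP 5.3.1, and SAP Section 2 states: "There are no statistical hypotheses for this study".

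**Conclusion.** The point holds in conditional form. The SAP prefers an undefined date that, for participants lost to follow-up, can be later than the last time rescue status was known, and nothing limits censoring to that earlier time. Where this happens, the rescue-free curve is biased upward.

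For gaps of 1 to 3 months, and with the illustrative 66% and 33% levels, the shift at Month 12 is:

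- about 0.2 to 1.0 points at 5–10% loss, which is roughly one to three of 30 participants;
- 0.7 to 2.1 points at 20% loss;
- 1.2 to 3.8 points if all 33% were lost to follow-up.

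Longer gaps add more: 1.0 to 7.6 points across the same loss rates at 6 months. The likely shift is small beside a sampling SD of about 9 to 10 points. No primary or secondary result, hypothesis test or sample size changes. This is a cheap improvement to a descriptive analysis and does not threaten the trial's conclusions.

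**What to change.** In SAP 5.3.4.2, replace the censoring sentence with: *Participants without nonstudy rescue IOP-lowering treatment in the study eye will be censored at the date of the last visit or contact at which concomitant medications and procedures were assessed.* With that wording the analysis no longer depends on what the study exit date means. Because SAP 5.4.1 and 6.3.7.2 also use the exit date, a one-line definition of it would help there too.

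The cost is one sentence and one derived date from data already collected, with no protocol amendment. Lost participants contribute slightly less follow-up time. Nothing changes for anyone who attends an exit visit.

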5.3.4.3. Hour 0 IOP Analyses

The descriptive summary for Hour 0 IOP values in a sitting position at baseline with corresponding change from baseline by visit through Month 12/Study Exit will be performed by treatment cohorts for the study eye in Bimatoprost SR and Lumigan 0.01% cohorts and pooled treatment cohorts for the fellow eye. The mean of the Hour 0 IOP and the Hour 0 IOP change from baseline for each visit will be presented graphically for the study eye in the Bimatoprost SR cohort.

5.4. Safety Analysis

Descriptive statistics will be used to summarize the safety data by cohorts based on the SAF. The safety parameters will include the following non-ocular safety parameters: non-ocular AEs and vital signs; ocular safety parameters: visual field examination, visual acuity, macroscopic conjunctival hyperemia assessment, biomicroscopy, dilated ophthalmoscopy (including optic disc assessment), pachymetry, gonioscopy (including angle assessment), and specular microscopy. Results from ocular safety assessments will be summarized by participants and listed, including scheduled and unscheduled assessments (if any). The results will be presented by treatment cohorts for the study eye and pooled treatment cohorts for the fellow eye. Unless

otherwise stated, the last nonmissing safety assessment before the first dose of study treatment will be used as the baseline for all analyses of that safety parameter.

5.4.1. Study Duration

The study treatment duration will be calculated as the number of days between the study exit date and Day 1 treatment administration day, inclusively (date of study exit or last visit available – Day 1 + 1).

5.4.2. Adverse Events (AEs)

Adverse Events will be coded using the MedDRA.

An AE is any unfavorable and unintended sign (including a clinically significant abnormal laboratory finding), symptom, or disease (new or exacerbated) temporally associated with the use of study treatment, whether or not considered related to the study treatment. An AE will be considered a treatment emergent adverse event (TEAE) if the AE began or worsened (increased in severity or became serious) on or after the date (and time, if known) of the first administration of study treatment. An AE will be considered a treatment-emergent serious adverse event (TESAE) if it is a TEAE that additionally meets any SAE criterion.

Adverse events will be classified into ocular AEs and non-ocular AEs. An ocular AE will be determined by the location information on the adverse event page in eCRF and thus are not limited to AEs with primary SOCs of eyes. Additionally, questions about adverse event relationships to study treatment and study administration procedure will be asked in eCRF, and the answers to these questions will be used together to derive the treatment related TEAE.

Ocular AEs will be tabulated by treatment cohorts for the study eye and pooled treatment cohorts for the fellow eye, and non-ocular AEs will be summarized by treatment cohorts for participants.

Overall summaries of adverse events will be provided on a per-participant basis by treatment cohorts for categories including the following:

- All TEAEs
- Treatment-related TEAEs
 - Related to study drug
 - Related to study drug administration procedure
- All serious TEAEs
- Treatment-related serious TEAEs
 - Related to study drug
 - Related to study drug administration procedure
- Any TEAE leading to Bimatoprost SR implant removal
- Any TEAE leading to study discontinuation
- Deaths

Any non-ocular TEAEs will be summarized by the primary SOC, PT, and severity including serious TEAEs by the primary SOC and PT, treatment related by SOC and PT and those leading to study discontinuation by the primary SOC and PT.

For incidences of treatment emergent ocular adverse events, summaries will be provided for the following categories:

- Any ocular TEAEs by SOC, PT, and severity
- Any treatment related ocular TEAEs by SOC and PT
- Any serious ocular TEAEs by SOC and PT
- Any ocular TEAEs leading to study discontinuation by SOC and PT
- Any ocular TEAEs resulting in Bimatoprost SR implant removal by PT
- Any corneal TEAEs of interest by PT (Related AEs of interest will be identified separately prior to database lock.)
- Any anterior segment inflammation TEAEs of interest by SOC and PT (Related AEs of interest will be identified separately prior to database lock.)

5.4.3. Vital Signs

Vital signs (systolic and diastolic blood pressure, pulse rate, and temperature) will be collected, but not analyzed.

5.4.4. Clinical Safety Laboratory Assessment

Laboratory assessments (blood and urine samples) will be collected at the Screening visit, but will not be analyzed.

5.4.5. Pregnancy Test

Pregnancy test will be performed but will not be analyzed.

5.4.6. Additional Safety Assessments

5.4.6.1. Best Correct Visual Acuity

Visual acuity tests will be performed at all visits except on Day 1 and at the Sleep Lab visits. Best corrected visual acuity (BCVA) is recorded in Snellen equivalent units on eCRF as 20/8, 20/10, 20/12.5, 20/16 ... or 20/800. An increase in the second number (denominator) in Snellen equivalent unit indicates worsening of visual acuity (VA) and a decrease indicates an improvement. For example, change from 20/32 to 20/40 is a worsening of VA by one line, 20/32 to 20/20 (note that 20/25 is in between) is an improvement by 2 lines.

The line change from baseline at each post-baseline evaluation can be calculated using the formula:

$$\text{Line Change} = 10 \times \left[\log_{10} \left(\frac{d_{BL}}{d_{PBL}} \right) \right]$$

where d_{BL} = denominator of the Snellen equivalent unit at baseline,

d_{PBL} = denominator of the Snellen equivalent unit at post-baseline.

The logarithmic value in the formula above needs to be rounded to the nearest tenth before proceeding to the calculation of the line change. A positive value indicates an improvement, a negative value indicates a worsening, and a zero indicates no change. For example, the line change for a Snellen equivalent unit at baseline of 20/25 followed by a Snellen equivalent unit of 20/80 at a post-baseline visit would be:

$$\text{Line Change} = 10 \times \left[\log_{10} \left(\frac{25}{80} \right) \right] = 10 \times (-0.5) = -5$$

representing a worsening of 5 lines in VA. Note that there are 4 Snellen equivalent units (20/32, 20/40, 20/50 and 20/63) between 20/25 and 20/80, thus moving from 20/25 to 20/80 is a worsening by 5 lines in VA because the denominator has increased.

The greatest line change in BCVA from baseline will be summarized with respect to number of line change categories. Categories will be summarized as change < -2, -2 ≤ change ≤ 2, and change > 2. The number and percentage of participant in each category will be presented by treatment cohorts.

5.4.6.2. Visual Field

Visual field examinations will be assessed by automated perimetry (using either Humphrey 24-2 full threshold program or 24-2 SITA Standard, or Octopus G1 or 24-2 and dynamic or normal strategy) at Screening, Baseline, Month 6, and Month 12/Exit. The same test methodology should be used throughout the entire study for a given participant. Visual field overall results will be recorded on the eCRF as normal or abnormal. Abnormal findings include enlargement of blind spot, superior arcuate scotoma, interior arcuate scotoma, paracentral scotoma, nasal step, central scotoma, generalized depression, and temporal scotoma and other. An eye may exhibit multiple abnormalities. Any post-baseline abnormal findings on visual field will be summarized by eye and by visit regardless of the machine type using number and percentage format to calculate incidences.

In addition, mean deviation or mean defect (MD) and change from baseline will also be recorded in decibels (dB), and will be analyzed by visit by machine type (Humphrey and Octopus respectively). If the machine type is different between baseline and post baseline visit, no change from baseline will be derived. If machine type is missing at post-baseline, but available at baseline, then it will be assumed using same machine type. For participants whose visual field were assessed by one machine type as recorded, the mean deviation or mean defect assessment with missing machine type will be imputed as assessments by the corresponding unique machine type.

